8.3.2 Contraception and Pregnancy Avoidance Measures

Reproductive toxicology studies have not been yet conducted and the risks of **HU6** on the fetus are unknown.

Male subjects are required to use one of the following acceptable forms of contraceptives during the study until 30 days after the last dose of study drug if they engage in sexual intercourse with a woman of childbearing potential:

- Condoms
- Sexual abstinence
- Vasectomy

For female subjects, non-childbearing potential requires being either surgically sterile (e.g., hysterectomy, bilateral tubal ligation, bilateral oophorectomy) or post-menopausal \geq 12 months of spontaneous and continuous amenorrhea with a follicle stimulating hormone (FSH) level > 40 IU/L in a female).

Women of childbearing potential are required to use one of the following acceptable forms of contraceptives during the study until final follow-up visit:

- Double-barrier methods of contraception; condoms with the use of caps (with spermicide) or with the use of intrauterine device (IUD) are acceptable.
- Hormonal contraceptives (oral, depots, patches, etc.) with a barrier method of contraception.
- Abstinence from sexual intercourse.
- A male partner who is sterile prior to the female subject's entry into the study and is the sole sexual partner for that female subject.
- Is with a same-sex partner and does not participate in bisexual activities where there is any risk of pregnancy.

Male subjects must not donate sperm from day 1 of dosing and for at least 30 days after the last dose of study drug.

Female subjects of childbearing potential must not donate ova during the study and for at least 30 days after the last dose of study drug.

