Eligible subjects will be randomized equally to 1 of the 4 following treatment groups (approximately 20 subjects per group):

- Group 1: matched placebo orally once daily for 61 days.
- Group 2: 150 mg HU6 orally once daily for 61 days.
- Group 3: 300 mg HU6 orally once daily for 61 days.
- Group 4: 450 mg HU6 orally once daily for 61 days.

The randomization will be blocked and stratified by HbA_{1c} (normal range versus between 5.7% and 9.0% inclusive).

Inclusion Criteria: Subjects must meet all the following inclusion criteria to be eligible:

- 1. Adult male or females, 28 to 65 years of age (inclusive) at the time of informed consent with BMI between 28.0 and 45.0 kg/m² (inclusive).
 - a. Female subjects of childbearing potential must be non-lactating, not pregnant as confirmed by a negative urine pregnancy test at Screening and agree to continue using an effective method of contraception for at least 4 weeks or barrier method for 2 weeks prior to first study drug administration until 30 days after the last dose of study drug.

- b. Female subjects of childbearing potential must not donate ova during the study and for at least 30 days after the last dose of study drug.
- c. Female subjects of non-childbearing potential must be surgically sterile (e.g., hysterectomy, bilateral tubal ligation, oophorectomy) or postmenopausal (no menses for >1 year with follicle stimulating hormone (FSH) >40 U/L at Screening).
- d. Male subjects who have not had a vasectomy and/or subjects who have had a vasectomy but have not had 2 post surgery negative tests for sperm must agree to use an acceptable method of contraception from time of first dose of study drug until 30 days after the last dose of the study drug, and to not donate sperm during the study and for at least 30 days after the last dose of study drug.
- 2. Inclusion as per investigator assessment of general medical status and as documented by medical history, physical examination, vital sign assessments, 12-lead ECG, clinical laboratory assessments, and general observations.
 - a. Subjects must be on stable doses of medications for underlying obesity-related conditions for at least 2 months prior to screening.
 - b. Subjects with diabetes may be treated with metformin, DPP-4 inhibitors, or sulfonylureas, but must be on stable doses for at least 2 months prior to screening.

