7.2 Inclusion Criteria

Subjects must meet all the following inclusion criteria to be eligible:

- 1. Adult male or females, 28 to 65 years of age (inclusive) at the time of informed consent with BMI between 28.0 and 45.0 kg/m² (inclusive).
 - a. Female subjects of childbearing potential must be non-lactating, not pregnant as confirmed by a negative urine pregnancy test at Screening and agree to continue using an effective method of contraception for at least 4 weeks or barrier method for 2 weeks prior to first study drug administration until 30 days after the last dose of study drug (Section 8.3.2).
 - b. Female subjects of childbearing potential must not donate ova during the study and for at least 30 days after the last dose of study drug.
 - c. Female subjects of non-childbearing potential must be surgically sterile (e.g., hysterectomy, bilateral tubal ligation, oophorectomy) or postmenopausal (no menses for >1 year with follicle stimulating hormone (FSH) >40 U/L at Screening).
 - d. Male subjects who have not had a vasectomy and/or subjects who have had a vasectomy but have not had 2 post surgery negative tests for sperm must agree to use an acceptable method of contraception from time of first dose of study drug until 30 days after the last dose of the

study drug, and to not donate sperm during the study and for at least 30 days after the last dose of study drug.

- 2. Inclusion as per investigator assessment of general medical status and as documented by medical history, physical examination, vital sign assessments, 12-lead ECG, clinical laboratory assessments, and general observations.
 - a. Subjects must be on stable doses of medications for underlying obesity-related conditions for at least 2 months prior to screening.
 - b. Subjects with diabetes may be treated with metformin, DPP-4 inhibitors, or sulfonylureas, but must be on stable doses for at least 2 months prior to screening.
 - c. At Screening, certain laboratory values may be outside the reference range if commensurate with the underlying obesity or associated metabolic dysfunction in the eligible subject (for example, dyslipidemia and hyperglycemia), unless these abnormalities suggest an underlying condition which may impact subject safety in the trial or interfere with the evaluation of HU6 or affect interpretation of the study results.

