7.4.1 Follow-up Procedures for Subjects Who Withdraw Prematurely

Subjects not completing the entire study should be fully evaluated when possible. All withdrawn subjects will be asked to report to the clinic for the Early Termination Visit within 2 weeks after their last dose of the study drug.

Subjects with ongoing AEs or AEs believed to be at least possibly related to study medication will continue to be followed until resolution or for 30 days as warranted by the nature of the AE.

The Investigator must make every attempt to follow-up on subjects who have withdrawn for any reason. When a subject is "lost to follow-up" (i.e., fails to return for study visits), a reasonable effort (3 documented phone calls or 2 phone calls and 2 text messages, on separate occasions, and a follow-up letter sent by registered mail) should be made to contact him/her to determine a reason for the failure to return. If the subject cannot be reached, they should be identified as "lost to follow-up" in the eCRF.

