8.2.10 Visit 10/ Day 73 (±2 days)

The following procedures will be conducted during the follow-up visit:

- Collect and process urine sample for laboratory tests (Section 11.5):
 - Routine UA (dipstick)
 - Pregnancy test (female subjects)
- Draw and process blood samples for laboratory tests (Section 11.5):
 - Hematology (CBC)
 - Comprehensive metabolic panel (includes LFT as well as routine chemistry panel; glucose, CPK, magnesium)
- Draw and process blood sample for PK (Section 9.1).
- Perform targeted physical examination including a neurological examination (Section 11.2).
- Measure and record vital signs including the InBody scale (Section 11.3).
- Perform 12-lead ECG (Section 11.6).
- Record AEs and concomitant medications.

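### Protocol 8.3.2 ends female contraception at the final follow-up visit (Day 71–75), but inclusion criterion 1a requires it until 30 days after the last dose (Day 91)

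*Protocol*

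**What the plan says.** Two parts of the protocol set an end date for contraception in women of childbearing potential.

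- **Inclusion criterion 1a.** The synopsis has these women agree to contraception from before "first study drug administration until 30 days after the last dose of study drug". Section 7.2 gives the same period and adds a cross-reference: "until 30 days after the last dose of study drug (Section 8.3.2".
- **Section 8.3.2**, the section cited, states that these women are "required to use one of the following acceptable forms of contraceptives during the study until final follow-up visit".

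The final follow-up visit is headed "Visit 10/ Day 73 (±2 days" in Section 8.2.10, and Section 5.3 places it 10 to 14 days after dosing ends. For women who stop early, Section 7.4.1 asks for "the Early Termination Visit within 2 weeks after their last dose of the study drug".

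Section 8.3.2 sets three other post-dose limits. Male contraception and the ban on sperm donation both run to 30 days after the last dose. Women of childbearing potential "must not donate ova during the study and for at least 30 days after the last dose of study drug". The section opens with the reason for the precautions: "Reproductive toxicology studies have not been yet conducted", so the risk to a fetus is not known.

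**The concern.** The same women have two different end dates for one obligation, and the shorter one sits in the section that the eligibility criterion refers to. Section 8.3.2 lists the acceptable methods, so it is a natural source for counselling during and after dosing.

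Read literally, 8.3.2 bars a woman from donating ova for 30 days after her last dose but no longer requires contraception of her after 10–14 days. A male participant must continue for the full 30 days. No rationale is given for a shorter female period, and the pattern within the section suggests a drafting slip rather than a choice.

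What is at stake is participant safety. If a site followed 8.3.2 alone, a woman could stop contraception inside the period that criterion 1a was written to cover, for a drug with no reproductive toxicology data. The last scheduled pregnancy test is also at Visit 10, so no planned test falls in the remaining days. That is context only, since it is true under either wording. No endpoint, analysis population, test or estimate is affected.

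**Working it through.** **Inputs**

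| Input | Value | Source (Protocol) |
|---|---|---|
| Last dosing day for completers | Day 61 | 6.2.1 |
| Follow-up visit after end of dosing | 10–14 days | 5.3 |
| Visit 10 | Day 73 ±2 | 8.2.10 |
| Contraception end, criterion 1a | last dose + 30 days | Synopsis; 7.2 |
| Contraception end, 8.3.2 | final follow-up visit | 8.3.2 |
| Early Termination Visit | within 2 weeks of last dose | 7.4.1 |

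**Step 1. Reproduce the protocol's own follow-up window.** 61 + 10 = Day 71 and 61 + 14 = Day 75. From the visit heading, 73 − 2 = Day 71 and 73 + 2 = Day 75. The two agree with each other and with the Day 71–75 stated in Section 5.3.

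**Step 2. Is there a later visit that could be meant?** The schedule in Section 8.1 ends at Visit 10. The 30-day periods for adverse event follow-up (11.7.3) and SAE reporting (11.8.2) are reporting periods, not visits. The final follow-up visit therefore cannot be read as Day 91.

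**Step 3. End date under criterion 1a.** 61 + 30 = Day 91.

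**Step 4. Gap for completers.**

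| Visit 10 on | Days after last dose | Gap to Day 91 |
|---|---|---|
| Day 71 | 10 | 20 days |
| Day 73 | 12 | 18 days |
| Day 75 | 14 | 16 days |

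The gap is more than half of the 30-day period throughout (16/30 = 53% to 20/30 = 67%).

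Visit 9a may fall on Day 60. If the last dose were then taken on Day 60 (an assumption) and Visit 10 stayed on Day 71–75, the gap would be 90 − 75 = 15 to 90 − 71 = 19 days, which is essentially the same.

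**Step 5. Gap for women who stop early.** The protocol does not say whether the Early Termination Visit counts as the final follow-up visit. If it does, it falls 0–14 days after the last dose, and the gap is 30 − 14 = 16 to 30 − 0 = 30 days. The upper end needs the visit to fall on the day of the last dose.

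**Step 6. Compare the limits within 8.3.2.**

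| Obligation | End point |
|---|---|
| Male contraception | 30 days after last dose |
| Sperm donation | 30 days after last dose |
| Ova donation | 30 days after last dose |
| Female contraception | final follow-up visit (10–14 days after last dose) |

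Only the last row differs.

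**The case against.** The strongest reply is that the 30-day duty already binds. Criterion 1a makes it a condition of entry, criterion 6 requires willingness to comply with the protocol, and Section 13.1.3 rules out waivers. Section 8.3.2 sets a minimum and does not say that women may stop at Visit 10. Someone who reaches 8.3.2 from Section 7.2 has just read the 30-day period. This stands as mitigation: the two texts can both be met by continuing for 30 days. It does not remove the mismatch, because criterion 1a records an agreement made at entry, while 8.3.2 states the rule to be followed afterwards and states it differently.

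Second, harm is not shown. The documents do not reveal which text sites use, and the consent pages were not available for review. That is correct, and no actual exposure is claimed here. A consent form that said 30 days would still leave the protocol at odds with itself.

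Third, the proposed change adds no later pregnancy test, and the protocol already has cover after Visit 10. Participants are to report adverse events for 30 days after discharge or early withdrawal (11.7.3), SAEs are reported until 30 days after last treatment (11.8.2), and pregnancies are reported within 24 hours of knowledge (11.8.4). This also stands, but these provisions detect and report events. They do not set how long contraception lasts.

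Fourth, the early-stopper range depends on an unstated reading, and Section 8 lets out-of-window visits be rescheduled with the medical monitor, so neither range is a hard bound. That is accepted. The completer figure is the one to rely on.

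**Conclusion.** The concern holds. Section 8.3.2 and criterion 1a give different end dates for female contraception, and no text reconciles them. For completers with a last dose on Day 61 and Visit 10 within its window, 8.3.2 is 16–20 days shorter (18 at the nominal Day 73). For early stoppers the gap is 16–30 days, on the assumption that the Early Termination Visit is their final follow-up visit. These are differences between two texts, not measured exposure.

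Confidence in the mismatch is high; its effect in practice is unknown. It should be corrected because it concerns an operative safety rule for a drug of unknown fetal risk, and criterion 1a only partly mitigates it.

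**What to change.** In Section 8.3.2, change the end point for women of childbearing potential from the final follow-up visit to 30 days after the last dose of study drug. This matches criterion 1a and the other three limits in the section, and it settles the early-stopper case because the period no longer depends on which visit counts as final. Leave criterion 1a unchanged in Section 7.2 and the synopsis. Check that the consent form and any counselling material also give 30 days.

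The cost is one line of protocol wording and a document check. No visit, test, sample-size or analysis change is needed.

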8.3.3 Lifestyle and Dietary Restrictions

Subjects will be instructed to maintain their same diet and activity/exercise level throughout the study as they had prior to participation in the study.

• Subjects should continue their typical dietary habits during study conduct. There is no need for dietary changes. Subjects should not start a weight reduction program while participating in the study.

• Subjects should continue their typical exercise routine during study conduct. However, strenuous exercise should be avoided for 48 hours prior to each blood collection for clinical laboratory tests. Strenuous exercise includes strength (weightlifting, barre, etc.) and speed-strength (boot camp, cross fit, etc.) activities. Exercise such as walking or a slow jog is permitted as long as it is within the subject's typical regimen.

Subjects must not smoke or vape more than 10 cigarettes per week and cannot smoke or vape starting 1 day before each study visit. Nicotine patches are allowed.

Subjects should avoid ingesting alcohol for 48 hours prior to each blood collection for clinical laboratory tests. At other times during the study, alcohol intake should not exceed 14 drinks per week for men and 7 drinks per week for women [1 drink = 4 ounces (120 mL) of wine or 12 ounces (360 mL) of beer or 1 ounce (30 mL) of hard liquor].

9 PHARMACOKINETIC ASSESSMENTS

9.1 Pharmacokinetic Sample Collection

Blood samples will be collected, and plasma samples prepared at the following times:

- On Day 1, 14, and 28: predose (trough) and approximately 2, 4, and 6 hours postdose.
- On Days 2, 7, 42, and 61: predose (trough) sample.
- One sample during Visit 10 or Early Termination.

9.2 Handling, Shipping, Storage and Analysis of Blood Samples

Please refer to the Laboratory Procedures Manual for more information about sample collection, processing, storage, and shipment.

9.3 Pharmacokinetic Parameters

The following PK parameters will be determined from concentration-time data:

- Population PK (PPK) analysis of HU6 parent and metabolites (DNP and M1). The following PK parameters will be calculated: C_{max}, T_{max}, t_{/2}, T_{lag}, AUC_{0-τ}, AUC_{0-∞}, CL/F, Vd/F, λz. Other PK parameters may be calculated, as data allow and appropriate.
- As data permit, noncompartmental analysis of HU6 parent and metabolites (DNP and M1). The following PK parameters will be calculated: C_{max}, AUC, and accumulation.

10 PHARMACODYNAMIC ASSESSMENTS

An overview of PD assessments is provided below. Refer to Section 8 for PD blood collection time points. Please refer to the Study Procedure Manual for more information about sample collection, processing, storage, and shipment.

10.1 Magnetic Resonance Imaging-Proton Density Fat Fraction (MRI-PDFF)

Magnetic Resonance Imaging Proton Density Fat Fraction (MRI-PDFF) is a non-invasive, quantitative biomarker to assess liver fat content (steatosis). The percentage of fat in the liver, or proton density fat fraction (PDFF), is being measured using MR: MRI-PDFF at baseline and end of treatment. Liver volume will be assessed from an axial T1 weighted or dual echo gradient echo images covering the entire liver. This advanced MRI technique measures the fraction of mobile protons in the liver attributable to liver fat (the PDFF), which is a direct measure of liver fat content and is a fundamental tissue property. Subjects should be fasting for 4 hours prior to the MRI-PDFF being performed, however, if they are not, the scan can still be performed. Should the MRI show incidental findings unrelated to the study evaluation, subjects will be notified of the findings and a written report provided and a recommendation for the subject to follow up with their primary physician.

10.2 Abdominal MRI

An MRI image will be taken of the abdominal region to assess total fat. The two primary measurements from this scan will estimate the total visceral adipose tissue (VAT), the type of fat stored within the body cavity, and the subcutaneous adipose tissue (SAT), the type of fat visible right underneath the skin.

10.3 Fibroscan®

The Fibroscan is a non-invasive medical device which estimates liver fat content (steatosis) and liver stiffness (fibrosis). The assay works by measuring shear wave velocity. A 50-MHz wave is passed into the liver from a small transducer on the end of an ultrasound probe. The probe also has a transducer on the end that measure the velocity of the shear wave (in meters per second) as this wave passes through the liver. The shear wave velocity is converted into liver stiffness, which is expressed in kilopascals (VCTE score). A second measurement is also taken that estimates hepatic steatosis through measuring the ultrasonic attenuation of the echo wave, termed the controlled attenuation parameter (CAP). Subjects will need to be fasting for 4 hours prior to the Fibroscan® being conducted.

10.4 One Way Liver Assays (OWL)

10.4.1 OWL – Metabolomics

This metabolomics assay extracts metabolites from volunteer plasma and serum to take a snapshot of cellular function. Liquid chromatography-mass spectrometry (LC-MS) metabolomics is used to identify serum biomarkers that differentiate normal liver and NAFLD and between NASH and NAFLD. The metabolomics profile also provides insight into cellular function and inflammation through the examination of various cellular metabolites that provide insight into key molecular pathways.

10.4.2 OWL – Lipidomics

Lipidomics is non-invasive blood assay that analyzes and identifies lipids in plasma and serum. These lipids will be separated and characterized via mass spectrometry and the analysis will include fatty acids, fatty acid derivatives, glycerolipids, glycerophospholipids, sphingolipids, and sterols.

10.5 Slow Off-rate Modified Aptamer (SomaScan)

SomaScan is a non-invasive blood assay. Blood plasma and serum samples will be assayed using oligonucleotide aptamers whose three-dimensional conformational shape binds specifically to a protein target of interest. Over seven thousand proteins will be assayed and quantified, enabling a proteomic snapshot of the body. Different mathematical models have been applied to large clinical data to establish algorithms with predictive value in cardiovascular health, metabolic rate, lean body mass, liver inflammation, cardiorespiratory fitness, and glucose tolerance.

10.6 Enhanced Liver Fibrosis (ELF)

The ELF assay is a non-invasive blood test that measures three markers of liver inflammation and fibrosis: hyaluronic acid, procollagen III amino-terminal peptide (PIIINP), and tissue inhibitor of matrix metalloproteinase 1 (TIMP-1). The values of these three markers, when used in conjunction with accompanying clinical data, are highly predictive of the inflammatory and fibrotic state of the liver, as evidenced by correlating the data with histology in larger clinical trials.

10.7 Exploratory Biomarkers

Blood samples will be obtained and separated into plasma and serum components from which separate 400 μ L aliquots will be drawn, labelled, and stored for future analysis of proteins, lipids, or gene expression that could assist in explaining the pharmacological actions of HU6.

11 SAFETY ASSESSMENTS

11.1 Adverse Events

Adverse events will be captured from the start of study-related procedures at Screening (including diagnostic assessments or after signing of ICF) onward during this study. Important medical events and conditions occurring prior to this period are not AEs; they will be captured within the medical chart and in the Medical History section of the Case Report Form.

11.2 Physical Examination

Height should be measured on a wall-mounted stadiometer at Screening.

Refer to Section 8 for physical examination time points.

Complete Physical: At study visits in which a complete physical examination is required, the investigator should perform a thorough examination of all body systems (exception: genitourinary and reproductive should be symptom-directed). Neurological examination should include the assessment of strength.

Targeted Exam: A targeted physical exam that is symptom-based. Based upon change to subject symptoms or visual findings; in addition, each exam should include a limited neurological evaluation of the strength of muscle groups. The commonly accepted method of evaluating muscle strength is the Medical Research Council Manual Muscle Testing scale. This method involves testing key muscles from the upper and lower extremities against the examiner's resistance and grading the patient's strength on a 0 to 5 scale accordingly:

- 0 No muscle activation
- 1 Trace muscle activation, such as a twitch, without achieving full range of motion
- 2 Muscle activation with gravity eliminated, achieving full range of motion
- 3 Muscle activation against gravity, full range of motion
- 4 Muscle activation against some resistance, full range of motion
- 5 Muscle activation against examiner's full resistance, full range of motion

